10.4.1.2. Reporting Other Safety Data

All of other safety measurements will be associated and summarized for each visit based on the CRF as the following:

Visit	Time Slices Definition
Screening	Screen
Period 1	Day -1, Period 1 Days 1-Day 14
Period 2	Period 2, Days 15-28
Follow-up	Follow-up

10.5. Appendix 5: Data Display Standards & Handling Conventions

10.5.1. Study Treatment & Sub-group Display Descriptors

Treatment Group Descriptions		
RandAll NG		Data Displays for Reporting
Code	Description and Footnotes for the Displays	Description
A	CAB 30 mg once daily x 14 days	CAB 30mg
B	RBT 300 mg once daily + CAB 30 mg once daily x 14 days	RBT 300mg + CAB 30mg

10.5.2. Baseline Definition & Derivations

10.5.2.1. Baseline Definitions

For all endpoints (except as noted in the table) the baseline value will be the latest pre-dose assessment.

Table 7 Baseline Definitions

Parameter	Study Assessments Considered as Baseline			Baseline Used in Data Display
	Screening	Day -1	Day 1 (Pre-Dose)	
Safety				
Labs	X	X		Day -1
ECG			X	Day 1 (Pre-Dose)
Vital Signs (blood pressure, and pulse rate)	X		X	Day 1 (Pre-Dose)

10.5.2.2. Derivations and Handling of Missing Baseline Data

Definition	Reporting Details
Change from Baseline	= Post-Dose Visit Value – Baseline

NOTES:

- Unless otherwise specified, the baseline definitions specified in Section 10.5.2.1 Baseline Definitions will be used for derivations for endpoints / parameters and indicated on summaries and listings.
- Unless otherwise stated, if baseline data is missing no derivation will be performed and will be set to missing.
- The baseline definition will be footnoted on all change from baseline displays.

10.5.3. Reporting Process & Standards

Reporting Process	
Software	

 • The currently supported versions of SAS and S-Plus software will be used. 	
Reporting Area	
HARP Server	: US1SALX00259-HARP PROD-US
HARP Area	: \ARPROD\GSK1265744\mid205712\Final
QC Spreadsheet	: \ARWORK\GSK1265744\mid205712\Final\Documents
Analysis Datasets	

 • Analysis datasets will be created according to Clinical Data Interchange Standards Consortium (CDISC) standards (SDTM IG Version 3.1.3 or higher vision & Analysis Data Model (ADaM) Implementation Guide (ADaM IG) Version 1.1 or higher dataset standards) 	
Generation of Rich Text Format (RTF) Files	

 • RTF files will be generated for Safety summary displays. 	

Reporting Standard
General

 • The current GSK Integrated Data Standards Library (IDSL) will be applied for reporting, unless otherwise stated: 
 ○ 4.03 to 4.23: General Principles ○ 5.01 to 5.08: Principles Related to Data Listings ○ 6.01 to 6.11: Principles Related to Summary Tables ○ 7.01 to 7.13: Principles Related to Graphics
Formats

 • All data will be reported according to the actual treatment the subject received unless otherwise stated. • GSK IDSL Statistical Principles (5.03 & 6.06.3) for decimal places (DP's) will be adopted for reporting of data based on the raw data collected. • Numeric data will be reported at the precision collected on the eCRF. • The reported precision from non eCRF sources will follow the IDSL statistical principles but may be adjusted to a clinically interpretable number of DP's.
Planned and Actual Time

 • Reporting for tables, figures and formal statistical analyses: 
 ○ Planned time relative to dosing will be used in figures, summaries, statistical analyses and calculation of any derived parameters, unless otherwise stated. ○ The impact of any major deviation from the planned assessment times and/or scheduled visit days on the analyses and interpretation of the results will be assessed as appropriate. • Reporting for Data Listings: 
 ○ Planned and actual time relative to study drug dosing will be shown in listings (Refer to IDSL Statistical Principle 5.05.1). ○ Unscheduled or unplanned readings will be presented within the subject's listings. ○ Visits outside the protocol defined time-windows (i.e. recorded as protocol deviations) will be included in listings but omitted from figures, summaries and statistical analyses.
Unscheduled Visits

 • Unscheduled visits will not be included in summary tables. • Unscheduled visits will not be included in figures. • All unscheduled visits will be included in listings.

Reporting Standard	
Descriptive Summary Statistics	
Continuous Data	Refer to IDSL Statistical Principle 6.06.1
Categorical Data	N, n, frequency, %
Reporting of Pharmacokinetic Concentration Data	
Descriptive Summary Statistics	Refer to IDSL Statistical Principle 6.06.1 Assign zero to NQ values (Refer to GUI_51487 for further details)
Reporting of Pharmacokinetic Parameters	
Descriptive Summary Statistics. (Un-Transformed)	N, n, arithmetic mean, 95% confidence interval (CI) for the arithmetic mean, SD, median, minimum, maximum and CV(%) 
 • $CV(\%) = (SD/mean) * 100$
Descriptive Summary Statistics. (Log _e Transformed)	N, n, geometric mean, 95% CI of geometric mean, standard deviation (SD) of logged data and between-subject geometric coefficient of variation (CVb (%)) will be reported. 
 • Geometric mean = exp (mean on log_e scale) • $CVb (\%) = \sqrt{(\exp(SD^2) - 1) * 100}$ [NOTE: SD = SD of log_e transformed data]
Parameters Not Being Log _e Transformed	Tmax
Listings	Include PK Parameters: Cmax, Tmax, C _τ , AUC(0-τ), t _{1/2} and CL/F.
Graphical Displays	

 • Refer to IDSL Statistical Principals 7.01 to 7.13. 	

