	
potential only)
 
 • Alcohol and drug screen (to include at minimum: amphetamines, barbiturates, cocaine, opiates, cannabinoids and benzodiazepines) • Urine or Serum hCG Pregnancy test (as needed for women of child bearing potential)

NOTES :
 
1. Details of Liver Chemistry Stopping Criteria and Required Actions and Follow-Up Assessments after liver stopping or monitoring event are given in Section 5.4.2 and Appendix 2.
	

Abbreviations:

RBC- Red blood cells, WBC- White blood cells, MCV- Mean corpuscular volume, MCH- Mean corpuscular hemoglobin, RDW- Red cell distribution width, BUN- Blood urea nitrogen, SGOT- Serum glutamic-oxaloacetic transaminase, SGPT- Serum glutamic pyruvic transaminase, CO₂ – Carbon dioxide, GGT- Gamma glutamyltransferase, CPK- Creatine phosphokinase

All laboratory tests with values that are considered clinically significantly abnormal during participation in the study or within 14 days after the last dose of study treatment should be repeated until the values return to normal or baseline. If such values do not return to normal within a period judged reasonable by the investigator, the etiology should be identified and the sponsor notified.

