9.4. Key Elements of Analysis Plan

Final analysis will be performed after the completion of the study and final datasets authorization.

Data will be listed and summarized according to GlaxoSmithKline reporting standards, where applicable. Listings will be sorted by subject, period, day, and time, noting treatment; summaries will be presented by treatment, day, and time.

Unless stated otherwise, descriptive summaries for continuous variables will include n, mean, standard deviation (SD), coefficient of variation for the mean (%CV), median, minimum, and maximum, geometric mean with associated 95% confidence interval (CI), and the between-subject CV (%CVb) for the geometric mean; whereas, n and percent will be used as summary statistics for categorical variables.

Baseline or pre-dose assessment is the last available assessment prior to time of the first dose unless it is specified otherwise. If there are multiple assessments collected on the same scheduled time, the average of these assessments will be used. For tabulated safety summaries, only the scheduled assessments will be included in the summary tables.

Version 9.3 or higher of the Statistical Analysis Software (SAS) system will be used to analyze the data as well as to generate tables, figures, and listings.

Complete details will be documented in the Reporting and Analysis Plan (RAP).

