
If ALT ≥ 3xULN AND bilirubin < 2xULN and INR ≤ 1.5:
 
 Repeat liver chemistries (include ALT, AST, alkaline phosphatase, bilirubin) and perform liver event follow up assessments within 24-72 hrs Monitor subjects weekly until liver chemistries resolve, stabilize or return to within baseline 	
total immunoglobulin G (IgG or gamma globulins).
 
 Serum acetaminophen adduct HPLC assay (quantifies potential acetaminophen contribution to liver injury in subjects with definite or likely acetaminophen use in the preceding week [James, 2009]). Liver imaging (ultrasound, magnetic resonance, or computerised tomography) and /or liver biopsy to evaluate liver disease; complete Liver Imaging and/or Liver Biopsy CRF forms.

- Serum bilirubin fractionation should be performed if testing is available. If serum bilirubin fractionation is not immediately available, discontinue study treatment for that subject if ALT ≥ 3xULN and bilirubin ≥ 2xULN. Additionally, if serum bilirubin fractionation testing is unavailable, **record presence of detectable urinary bilirubin on dipstick**, indicating direct bilirubin elevations and suggesting liver injury.
- All events of ALT ≥ 3xULN and bilirubin ≥ 2xULN (>35% direct bilirubin) or ALT ≥ 3xULN and INR > 1.5, if INR measured, which may indicate severe liver injury (possible 'Hy's Law'), **must be reported as an SAE (excluding studies of hepatic impairment or cirrhosis)**; INR measurement is not required and the threshold value stated will not apply to subjects receiving anticoagulants
- Includes: Hepatitis A IgM antibody; Hepatitis B surface antigen and Hepatitis B Core Antibody (IgM); Hepatitis C RNA; Cytomegalovirus IgM antibody; Epstein-Barr viral capsid antigen IgM antibody (or if unavailable, obtain heterophile antibody or monospot testing); Hepatitis E IgM antibody
- PK sample may not be required for subjects known to be receiving placebo or non-GSK comparator treatments. Record the date/time of the PK blood sample draw and the date/time of the last dose of study treatment prior to blood sample draw on the CRF. If the date or time of the last dose is unclear, provide the subject's best approximation. If the date/time of the last dose cannot be approximated OR a PK sample cannot be collected in the time period indicated above, do not obtain a PK sample. Instructions for sample handling and shipping are in the SRM.

References

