12.7. Appendix 7: Toxicity Management

ANEMIA

Grade 1 (mild) hemoglobin decrease:

Any hemoglobin decrease meeting the definition of Grade 1 must be repeated with the following additional tests:

1. peripheral blood smear
2. indirect bilirubin (abnormal if increased >50% from baseline)
3. haptoglobin (abnormal if ≤ 25 mg/dL)
4. reticulocyte count (abnormal if $\geq 4\%$)

If the additional tests are within the normal range, subjects may continue study medication. If one or more of the additional tests is abnormal or suggestive of hemolytic anemia as specified above, subjects will permanently discontinue study medication and be withdrawn from the trial. Subjects should be followed up until resolution of anemia.

Grade 2 (moderate) hemoglobin decrease:

Any hemoglobin decrease meeting the definition of Grade 2 must be repeated with the following additional tests:

5. peripheral blood smear
6. indirect bilirubin (abnormal if increased >50% from baseline)
7. haptoglobin (abnormal if ≤ 25 mg/dL)
8. reticulocyte count (abnormal if $\geq 4\%$)

If the additional tests are within the normal range, subjects may continue study medication. If one or more of the additional tests is abnormal or suggestive of hemolytic anemia as specified above, subjects will permanently discontinue study medication and be withdrawn from the trial. Consultation with a Hematologist should be considered. Subjects should be followed up until resolution of anemia.

Grade 3 (severe) or Grade 4 (potentially life threatening) hemoglobin decrease:

Any hemoglobin decrease meeting the definition of Grade 3 or 4 must be repeated with the following additional tests:

9. peripheral blood smear
10. indirect bilirubin
11. haptoglobin
12. reticulocyte count

Subjects will permanently discontinue study medication and be withdrawn from the trial. Consultation with a Hematologist should be considered. Subjects should be followed up until resolution of anemia.

TOTAL BILIRUBIN ELEVATION

Grade 1 (mild) bilirubin elevation (1.1 - 1.5 times ULN) or Grade 2 (moderate - 1.6-2.5 times ULN):

Any bilirubin value above the upper limit of normal must be repeated and fractionated (direct and indirect bilirubin). Subjects may continue study medication. Subjects should be followed up until resolution (return to baseline) of elevation.

Grade 3 (severe – 2.6-5.0 times ULN) or 4 (life-threatening - > 5.0 times ULN) bilirubin elevation:

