10.11.4. Safety Tables

Safety Tables					
No.	Population	IDSL / TST ID / Example Shell	Title	Programming Notes	Deliverable [Priority]
Adverse Events					
2.1.	Safety	LAI117010/ Table 2.1	Summary of Exposure Data	By subject and treatment	SAC
2.2.	Safety	LAI117010/ Table 2.2	Relationship of Adverse Event System Organ Classes, Preferred Terms, and Verbatim Text		SAC
2.3.	Safety	LAI117010/ Table 2.3	Summary of All Adverse Events by Treatment		SAC
2.4.	Safety	LAI117010/ Table 2.4	Summary of Drug-Related Adverse Events by Treatment		SAC
2.5.	Safety	LAI117010/ Table 2.5	Listing of Serious Adverse Events	By subject and treatment.	SAC
2.6.	Safety	LAI117010/ Table 2.6	Listing of Adverse Events Leading to Permanent Discontinuation of Study Drug or Withdrawal from Study	By subject and treatment	SAC
Labs					
2.7.	Safety	LAI117010/ Table 2.7	Listing of Reference Ranges for Clinical Laboratory Tests		SAC
2.8.	Safety	LAI117010/ Table 2.8	Summary of Clinical Haematology Laboratory Data by Treatment and Time		SAC
2.9.	Safety	LAI117010/ Table 2.9	Summary of Clinical Chemistry Laboratory Data by Treatment and Time		SAC
2.10.	Safety	LAI117010/ Table 2.10	Summary of Treatment Emergent Grade 2 or Higher Lab Abnormalities by Treatment	Summary of Treatment Emergent Lab toxicity only.	SAC
2.11.	Safety	LAI117010/ Table 2.11	Listing of Treatment Emergent Grade 2 or Higher Lab Abnormalities	By subject and treatment	SAC
2.12.	Safety	CP_LB5	Summary of All Urinalysis Data		SAC

Safety Tables					
No.	Population	IDSL / TST ID / Example Shell	Title	Programming Notes	Deliverable [Priority]
Vital Signs					
2.13.	Safety	LAI117010/ Table 2.13	Summary of Vital Signs by Treatment and Time	Include BP and HR only.	SAC
2.14.	Safety	LAI117010/ Table 2.14	Summary of Change from baseline in Vital Signs by Treatment and Time	Include BP and HR only.	SAC
2.15.	Safety	LAI117010/ Table 2.15	Listing of Vital Signs for Subjects with Abnormalities of Potential Clinical Importance	By subject and treatment	SAC
ECGs					
2.16.	Safety	LAI117010/ Table 2.16	Summary of ECG Findings		SAC
2.17.	Safety	LAI117010/ Table 2.17	Summary of ECG Values by Treatment and Time		SAC
2.18.	Safety	LAI117010/ Table 2.18	Summary of Change from Baseline in ECG Values by Treatment and Time		SAC
2.19.	Safety	LAI117010/ Table 2.19	Summary of Category of QTc Data by Treatment and Time		SAC
2.20.	Safety	LAI117010/ Table 2.20	Summary of Category of QTc Change from Baseline by Treatment and Time		SAC

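### The scheduled-only rule also governs Table 2.10, so a subject whose Grade 2 or higher lab value first appears on an off-schedule repeat is left out of the by-treatment count

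*SAP*

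**What the plan says.** SAP 10.5.3, under Unscheduled Visits, sets a general rule: "Unscheduled visits will not be included in summary tables". The same block keeps unscheduled visits out of figures and adds: "All unscheduled visits will be included in listings". Protocol 9.4 agrees: "For tabulated safety summaries, only the scheduled assessments will be included in the summary tables". Neither passage exempts any table.

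SAP 10.11.4 lists Table 2.10 as "Summary of Treatment Emergent Grade 2 or Higher Lab Abnormalities by Treatment". Its only programming note restricts it to treatment-emergent laboratory toxicity. Display 2.11 is the by-subject listing of the same abnormalities.

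The protocol generates results off the visit schedule when a value is abnormal:

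- Section 7.3.6: clinically significant abnormal laboratory values, up to 14 days after the last dose, "should be repeated until the values return to normal or baseline".
- Appendix 2, liver events: repeat within 24 hours or within 24 to 72 hours, depending on bilirubin and INR. Follow-up is then twice weekly in the first case; in the second, "Monitor subjects weekly until liver chemistries resolve, stabilize or return to within baseline".
- Appendix 7, anaemia: "Any hemoglobin decrease meeting the definition of Grade 1 must be repeated with the following additional tests", with the same requirement at Grades 2 to 4.
- Appendix 7, bilirubin: "Any bilirubin value above the upper limit of normal must be repeated and fractionated (direct and indirect bilirubin").

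**The concern.** Restricting a by-visit table to scheduled visits is sound, because otherwise retested subjects would weigh more heavily in visit means. That reason does not apply to Table 2.10, which asks whether a subject reached a given toxicity grade on a given treatment. There, the repeat tests prompted by an abnormal result are the ones most likely to show the worst value, and the rule removes them.

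Comparing the safety of CAB alone with CAB plus RBT is a secondary objective. Table 2.10 is the only planned by-treatment tabulation of graded laboratory toxicity. Its count could fall short of what listing 2.11 shows for the same subjects. Protocol 4.6.2 names neutropenia as a common effect of RBT, so any shortfall might fall more on the test treatment. The documents give no data to say whether it would.

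**Working it through.** The plan states no figure on this point, so the check sets the passages side by side and then gives the scale.

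**Step 1: which laboratory draws are scheduled.** The schedule table in SAP Appendix 3 has displaced columns in the text available, so the days are inferred. The laboratory row lines up with the unit-admission row, and Protocol 4.2 puts those readmissions on Days 13 and 27. Scheduled post-dose draws are then about Day 13, about Day 27, and early withdrawal/follow-up. A value obtained at any of these enters Table 2.10.

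**Step 2: when a subject is missed.** Grades are from Protocol Appendix 6. The values are illustrations. In each case the repeat is on a later, unscheduled day and no other scheduled draw reaches Grade 2.

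| Test | Scheduled value | Unscheduled repeat | Counted in Table 2.10? |
|---|---|---|---|
| ANC, x10^9/L | 0.90 (Grade 1: 0.800 to 1.000) | 0.70 (Grade 2: 0.600 to 0.799) | No |
| Haemoglobin, male, g/dL | 10.5 (Grade 1: 10.0 to 10.9) | 9.8 (Grade 2: 9.0 to <10.0) | No |
| ALT, x ULN | 3.2 (Grade 2: 2.5 to <5.0) | 11 (Grade 4: 10.0 or more) | Yes, from the scheduled value |

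In the first two rows the subject is absent from Table 2.10 and present in listing 2.11. The ANC of 0.90 is also below the stopping threshold of 1 x10^9/L in Protocol 5.4.4, so the omitted subject is one who met a stopping criterion. In the ALT row the count is correct, and only a maximum-grade column, if there is one, would be too low.

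**Step 3: direction.** Let S be the subjects with a Grade 2 or higher post-baseline value at a scheduled draw, and U those with one at an unscheduled draw. Table 2.10 counts |S|; the complete count is |S ∪ U|. Since |S| ≤ |S ∪ U|, the rule can leave the count unchanged or lower it, but never raise it.

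**Step 4: size per subject.** With the planned 15 subjects on a treatment, one omission is 1/15 = 6.7 percentage points. If only 12 reached that period, it is 1/12 = 8.3 points.

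**Step 5: chance that it happens.** The documents do not give the probability p that a subject's Grade 2 or higher value is seen only off schedule. For assumed values, and treating subjects as independent, P(at least one of 15) = 1 − (1 − p)^15:

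| Assumed p | P(at least one omitted) |
|---|---|
| 1% | 14% |
| 2% | 26% |
| 5% | 54% |
| 10% | 79% |

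**The case against.** The strongest reply is that nothing is lost from the report. Unscheduled values appear in listing 2.11, in Listings 11 and 12 with their grades, and in the liver-event listing 2.25. Abnormalities judged clinically significant are adverse events under Protocol 12.4.1 and enter Tables 2.3 and 2.4. With about 15 subjects a reader can go through every case. The protocol and SAP also agree with each other, and repeats at the same time point are averaged into the summaries (SAP 10.6.1). All of this stands and limits the weight of the point. It does not close the gap: averaging does not reach repeats on later days, adverse events depend on the investigator's judgement rather than on the laboratory grade, and a summary table should not have to be rebuilt from listings.

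Several stronger readings are tempting, but the documents do not support them:

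- *Every Grade 2 value away from Days 13 and 27 counts as zero.* The early-withdrawal/follow-up draw is scheduled and is not barred.
- *A rise in ALT after a liver stopping event drops the subject from the count.* The stopping threshold of 3 x ULN is already Grade 2, so a scheduled value that triggers the repeat is counted.
- *The QTc category tables have the same fault.* Tables 2.19 and 2.20 are laid out by treatment and time, so the scheduled-only rule suits them, and QTc outliers are listed separately.
- *A follow-up visit later than 14 days after the last dose is dropped.* SAP 10.5.3 omits only out-of-window visits recorded as protocol deviations, and the protocol gives the follow-up timing only approximately.
- *Table 2.10 and listing 2.11 will disagree on maximum grade.* The layout of Table 2.10 comes from another study's table that the documents do not reproduce, so whether it reports maximum grade is unknown.

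**Conclusion.** The point holds for Table 2.10. As written, the rule makes that table a count of Grade 2 or higher values seen at scheduled draws, although the protocol moves the follow-up of abnormal results off schedule. The error can only run downward. It costs 6.7 percentage points for each subject whose Grade 2 value is first and only seen off schedule. How often that happens cannot be derived from the documents.

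The conclusion rests on two assumptions: that the scheduled draws are as inferred from the displaced schedule table, and that the rule will be applied literally, since no exception is stated. The effect is confined to one secondary safety summary. It is an avoidable choice of data for one table; the two documents do not contradict each other, and the report loses no data.

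**What to change.** In SAP 10.5.3, limit the scheduled-only rule to by-visit tables, including 2.8, 2.9, 2.13, 2.14 and 2.17 to 2.20. Add that Table 2.10 uses the worst post-baseline value per subject and treatment from all results, scheduled and unscheduled. Because SAP 10.4.1.2 places laboratory results by visit, also say how an unscheduled result is assigned to a treatment. The date/time rule that SAP 10.4.1.1 uses for adverse events would serve. Record the change in SAP 2.1, which at present reports no departures from the protocol, as a change from Protocol 9.4. A worst-post-baseline row in the QTc category tables is optional.

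The cost is a few sentences and a small programming change; the data are already collected and graded. The downside is that retested subjects have more chances to be flagged, which is normal for a worst-value table and can be stated in a footnote.

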10.6. Appendix 6: Derived and Transformed Data

10.6.1. General

Multiple Measurements at One Time Point

- Mean of the measurements will be calculated and used in any derivation of summary statistics but if listed, all data will be presented.

Study Day

- Calculated as the number of days from Treatment start date :
 - Ref Date = Missing → Study Day = Missing
 - Ref Date < Treatment start Date → Study Day = Ref Date – Treatment start Date
 - Ref Date ≥ Treatment start Date → Study Day = (Ref Date – Treatment start Date) + 1

